
Our rationale for selecting an extended duration treatment is as follows. First, we have shown, in a placebo-controlled randomized trial with general population smokers, that 24-weeks of transdermal nicotine, vs. the standard 8-weeks, increases 6-month quit rates by an OR of 1.81 (32% vs. 20%; [name] et al., 2010b). Second, and importantly, extending treatment with the nicotine patch to 24-weeks significantly helps smokers with high levels of nicotine dependence and cognitive impairment, in particular, to overcome their liability to relapse (see below). While extended therapy with transdermal nicotine did not offset the effect of depression symptoms on relapse rates, the quit rate among depressed smokers in extended treatment was almost 2-times

higher than it was for depressed smokers in standard treatment (see below). Third, we showed in our placebo-controlled randomized clinical trial with general population smokers ([name] et al., 2010b) that extending treatment with transdermal nicotine to 24-weeks (vs. 8-weeks) significantly reduced the probability that smokers would experience a lapse and, importantly, increased the likelihood that smokers would recover to abstinence following a lapse. Extended duration treatment offered smokers who lapsed the opportunity to re-start their quit attempt and eventually achieve abstinence. Thus, extended duration varenicline may be particularly efficacious at addressing the barriers to cessation that are evident among cancer patients.

CHARACTERISTICS OF THE STUDY POPULATION

1. Target Population

Three hundred seventy-four adult male and female smokers 18 years of age or older who have been diagnosed with cancer (all sites) within the past 5 years will complete the study.

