Smoking status is assessed using the timeline follow-back method (Brown et al., 1998) as done previously (Lerman et al., 2004; [name] et al., 2010b) and by using breath CO to verify self-report. Participants are considered abstinent if they self-report abstinence (not even a puff of a cigarette) for >7 days prior to the Week 24 and 52 assessment and have a breath CO of <10ppm at the time-point (SRNT, 2002; Hughes et al., 2003). As per convention, participants are assumed to be smoking if they self-report to be smoking at the time-point, cannot be reached to provide data at the time-point, fail to provide a breath sample at the time-point, or provide a breath sample at the time-point that is >10ppm (SRNT, 2002).

Cessation/Smoking Rate: Daily smoking (presence and rate) will be assessed at each visit after Intake Session with the well validated timeline followback method (TLFB). These data can be used to assess

the timing and rates of lapses (smoking episodes not lasting 7 days), recovery events (return to abstinence), and relapse events, as well as to monitor changes in smoking rates (i.e., # cigarettes/day). These data will also be used to compute and assess secondary measures of smoking cessation (e.g., continuous and prolonged abstinence).

Carbon Monoxide (CO) Test: Carbon monoxide will be measured at each in-person visit to confirm smoking status.

Other Smoking Measures (secondary)

As per recommendations (Hughes et al., 2003), we will also assess: prolonged abstinence to Weeks 12, 24, and 52 (relapse is 7 consecutive days of self-reported smoking, after a 2-week grace period), continuous abstinence at Weeks 12, 24, and 52 (no smoking between the quit day and follow-up), time to 7-day relapse (no grace period), smoking rate, and lapse (smoking episodes < 7 days) and recovery (return to 24-hour abstinence) events.

Quality of Life (QOL)

The Short-Form Health Survey (SF-12) will assess QOL (Ware et al., 1996). This scale yields physical and mental subscales, has been used to assess cancer patient QOL (McCorkle et al., 2009), has demonstrated validity and reliability (Gandek et al., 1998), and has been used in smoking cessation trials with cancer patients ([name] et al., 2010a). The SF-12 will be administered at all visits following the Intake Session.

2. Statistical Analysis

Power

Power is provided for the primary aims since the exploratory aim is hypothesis generating. All comparisons are 2-sided.

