Aim 1: Compare standard varenicline treatment (12-weeks active then 12-weeks placebo) to extended varenicline treatment (24-weeks active) for treating nicotine dependence among cancer patients. The hypothesized effect of treatment arm (i.e., the difference in quit rates between subjects receiving standard or extended treatment) will be tested by a treatment arm term in a binomial family with logit link (logistic regression) model that possibly includes terms for covariates. Outcomes of the logistic regression analyses will be characterized by odds ratios (e.g., odds of quitting smoking) and 95% confidence intervals. Although quit-rates at the end of 24 and 52 weeks will represent our primary outcome variables, similar logistic regression analyses will be performed for other assessments of quit rates (e.g., quit rates at Weeks 12 and 26). This model will be used for measures of prolonged and continuous abstinence as well. In addition, as many participants will fail to become completely abstinent, the negative binomial family log link for count data will be used to examine the main effects of treatment arm on changes in smoking rate. Time to (recurrent) event models will be fitted using Cox regression, stratified by event sequence, as in [name] et al. (2010).

Aim 2: Assess effects of extended varenicline therapy on QOL and varenicline side effects. Repeated-measures MANOVA will examine differences across treatment arms in mental and physical QOL over the trial. Covariates will be included, such as medical treatment history. We will compare treatment arms in terms of the frequency of severe side effects (individual and total). Logistic regression will test against the lower boundary on percent reporting only mild-moderate (i.e., < severe) side effects. The hypothesis test for equivalence is whether the OR is out of the prescribed range for the difference between the treatment arms.

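### A lapse is defined by how the episode ends, so every completed lapse recovers by definition, and lapse and recovery comparisons can mislead

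*Combined protocol and SAP*

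**What the plan says.** Smoking is recorded by day with the timeline follow-back. Under Cessation/Smoking Rate: "Daily smoking (presence and rate) will be assessed at each visit after Intake Session". The same paragraph says the data can be used to study "the timing and rates of lapses (smoking episodes not lasting 7 days), recovery events (return to abstinence), and relapse events". Under Other Smoking Measures (secondary), the list includes "lapse (smoking episodes < 7 days) and recovery (return to 24-hour abstinence) events". For prolonged abstinence, "relapse is 7 consecutive days of self-reported smoking, after a 2-week grace period". Time to 7-day relapse, without the grace period, is a separate secondary outcome. Outcome Assessments also lists lapse and recovery events, without defining them.

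For analysis, Aim 1 under Data Analysis says only: "Time to (recurrent) event models will be fitted using Cox regression, stratified by event sequence", following a cited 2010 paper. It gives no time origin, no risk set and no rule for episodes that become relapses.

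The Background section on extended-duration varenicline reports that the earlier extended-patch trial "increased the likelihood that smokers would recover to abstinence following a lapse", as part of the third reason for extending treatment.

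**The concern.** Both definitions of a lapse depend on what happens after the episode starts. An episode that stops in time is a lapse, and one that reaches day 7 is a relapse. The stopping is itself the recovery, so failure to recover after a lapse cannot be observed once the episode is complete.

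Two things follow. The quantity the Background relies on, the likelihood of recovery after a lapse, cannot differ between arms under these definitions. And if extended treatment turns would-be relapses into short episodes, each converted episode adds a lapse to the extended arm. A real benefit would then appear as more lapses, and a true reduction in how often smoking restarts could be masked.

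**Working it through.** **The identity.** Take an episode to be a run of consecutive smoking days, which the plan implies but does not state. A run shorter than 7 days that has ended was followed by a smoke-free day. At daily resolution that is a return to 24-hour abstinence. So P(recovery | completed lapse) = 1 in each arm, whatever the rates. The only exceptions are episodes still open when data end. In a one-year simulation without dropout (assumed onset 0.02 per day) these were 0.2% to 0.4% of lapses.

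**Inputs for size.** The documents give no lapse or recovery rates, and no power figure rests on them, so there is no plan figure to reproduce. Assumption: on each day of an episode there is a constant chance r that the next day is smoke-free, and onset is equal in the two arms. Range for r, standard vs extended: 0.08 vs 0.12, 0.10 vs 0.15, 0.20 vs 0.30.

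**Lapse count.** P(episode is a lapse) = 1 − (1 − r)^6, and P(relapse) = (1 − r)^6. The onset reduction that would be fully masked is 1 − 1/ratio.

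| r, standard vs extended | Lapse share of episodes | Lapse ratio at equal onset | Relapse share of episodes | Onset reduction masked |
|---|---|---|---|---|
| 0.08 vs 0.12 | 0.394 vs 0.536 | 1.36 | 0.606 vs 0.464 | 27% |
| 0.10 vs 0.15 | 0.469 vs 0.623 | 1.33 | 0.531 vs 0.377 | 25% |
| 0.20 vs 0.30 | 0.738 vs 0.882 | 1.20 | 0.262 vs 0.118 | 16% |

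Middle row: 1 − 0.90^6 = 0.469, 1 − 0.85^6 = 0.623, and 0.623/0.469 = 1.33. A true 25% cut in onset gives 0.75 × 1.33 = 1.00.

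**Time to recovery.** Among episodes already known to end by day 6, the chance of recovering on day k, given not yet recovered, is r(1 − r)^(k−1) / [(1 − r)^(k−1) − (1 − r)^6].

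- On day 1 in the middle scenario this is 0.10/0.469 = 0.213 vs 0.15/0.623 = 0.241, a ratio of 1.13. The unconditioned ratio is 0.15/0.10 = 1.5.
- On day 6 it equals 1 in both arms.

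A Cox model was fitted to the expected day-by-day counts (6,000 episodes per arm), first with all episodes from onset and censoring at day 7, then with completed lapses only. The two figures in each cell are for Breslow and Efron ties.

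| r | HR, all episodes from onset | HR, lapses as defined |
|---|---|---|
| 0.08 vs 0.12 | 1.50 / 1.53 | 1.06 / 1.07 |
| 0.10 vs 0.15 | 1.50 / 1.54 | 1.07 / 1.09 |
| 0.20 vs 0.30 | 1.50 / 1.59 | 1.17 / 1.22 |

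Simulated samples over the same range scattered around these values, from about 1.03 to 1.2 for lapses as defined and about 1.5 to 1.6 from onset. With larger assumed contrasts (0.10 vs 0.20 and 0.15 vs 0.30) the HR fell from 2.05 and 2.09 to 1.20 and 1.28.

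**The case against.** The strongest reply is that the plan never commits to analysing recovery only among completed lapses. Its other wording treats recovery simply as a return to abstinence and does not tie it to a preceding lapse, so recovery from longer episodes is not excluded. The Cox models defer to a cited paper. The Background reports that the likelihood of recovery was higher with extended treatment in the earlier trial, so it was not fixed at 1 there. If that trial's method is the one followed, the working risk set may already start at onset. No passage plans a comparison of the proportion of lapses that recover, and no hypothesis or power figure depends on these events.

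Much of this stands, and it limits the point. A reader might infer that the recovery comparison is empty. It is not: only the proportion is degenerate, while time to recovery still varies over 1 to 6 days and its contrast is weakened rather than removed. A reader might also infer that the trial would hide or reverse the benefit of extended treatment. The documents do not support that, because time to 7-day relapse is a separate outcome and would show the benefit. In the middle scenario relapses fall from 53% to 38% of episodes.

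The reply does not remove the written definition. It appears twice, both times by how long the episode lasted, and neither the outcome sections nor the analysis section states an onset-based event or risk set.

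**Conclusion.** The point holds as a defect in secondary outcome definitions. That every completed lapse recovers needs no assumed rates beyond daily data and an episode being a run of smoking days. Nor does the direction of the lapse count: at equal onset it rises in the arm that recovers faster. The sizes are illustrative. They rest on a constant daily recovery chance between 0.08 vs 0.12 and 0.20 vs 0.30 and on equal onset.

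Whether the fitted Cox models would actually be conditioned on the episode's outcome cannot be settled from the documents, since the risk set is left to a cited paper. The attenuation is therefore what follows if lapses as defined are used. The Week 24 and Week 52 abstinence outcome and time to 7-day relapse do not use the lapse label and are unaffected. This should be corrected before analysis, but it does not threaten the trial's main conclusion.

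**What to change.** In Outcome Assessments and Other Smoking Measures (secondary), and in the matching sentence under Cessation/Smoking Rate:

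- **Lapse:** the first day of any smoking after at least 24 hours of abstinence, however long the episode then lasts.
- **Recovery:** the first 24-hour abstinence after lapse onset.
- **Relapse:** an episode that reaches 7 consecutive smoking days.

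In the Aim 1 analysis text, count every onset as the lapse event. Put every onset in the recovery risk set from its first day, with episodes that reach day 7 counted as not recovered by day 7. State the time origin and risk set in the plan itself instead of leaving them to the cited paper.

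The cost is a few sentences and a recode of timeline follow-back data that will be collected anyway. No visit, measure or primary outcome changes. The downside is that lapse counts will rise in both arms, because long episodes are now included.

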Quit Day Session (Week 1): At Week 1, participants will receive a 30-minute in-person “quit-day” session to review the initial quit attempt, identify potential reasons for relapse, and review a plan for avoiding tempting situations.

Relapse Prevention Sessions (Weeks 4, 8, 12, 14, and 18): Participants will then receive 5 additional 20-minute sessions (in-person or over the telephone) at Weeks 4, 8, 12, 14, and 18 which either reinforce success and review the quit plan or reestablish a quit date and restart the cessation process. The sessions are designed to enhance awareness of the harmful effects of smoking, assist the person in developing skills to quit and avoid relapse, and instruct the smoker on varenicline use. All sessions may be audio-taped and a random 15% of sessions are assessed for protocol adherence. The counselor is blind to randomization.

Varenicline or Placebo Treatment (Weeks 0-24).

Varenicline will be used in accordance with FDA approved labeling: Day 1-Day 3 (0.5mg once daily); Day 4-Day 7 (0.5mg twice daily); and Day 8-Day 84 (1.0mg twice daily). On Day 85, participants randomized to standard therapy will be given placebo pills (resembling the 1.0mg pills), while extended therapy participants will continue with active varenicline (1.0mg twice daily). Participants will take this medication until Day 168. Extended therapy was defined as 24 weeks to be consistent with previous trials ([name] et al., 2010b).

If a participant is not able to attend a medication pick up visit (Week 4 or Week 12), the session will be completed over the phone and, if eligible, one week of study medication will be mailed to the participant from the research pharmacy. Participants will need to schedule a brief appointment in-center to complete a blood pressure evaluation before additional study medication is dispensed (session blood pressure procedures apply). If the Week 4 or Week 12 assessments cannot be completed over the phone within the session window, participants will be invited to a brief in-center appointment for a side effects assessment and blood pressure evaluation before additional study medication is dispensed (session side effects and blood pressure procedures apply).

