As in our past (Patterson et al., 2009; [name] et al., 2011) and ongoing (U01 DA020830) varenicline trials, a checklist and open-ended questions assess the incidence and severity of varenicline-related side effects at all time-points following the Intake Session. These assessments monitor safety, and dose reductions or suspension of medication may be indicated based on the side effect reporting. Side effects will be a study outcome and a covariate; overall frequency, changes from pre-treatment baseline (Pre-Quit) and the presence of specific side effects will all be tracked. This measure includes potential varenicline-related psychiatric events (Kuehn, 2008) and cardiovascular side effects.

Varenicline Adherence

Medication adherence will be assessed by self-report using a time-line follow-back method and by pill count and collection of used blister packs at each visit as in past varenicline trials (e.g., Gonzales et al., 2006; Jorenby et al., 2006; Ebbert et al., 2009; Niaura et al., 2008). We will also collect blood (10mL) from 50% of participants enrolled at Penn at Week 4 to assess varenicline levels as an adherence measure and to examine the validity of self-report and pill count data. An adherence measure will represent the proportion of total dose taken (adherence = > 80% of dose taken based on self-report, pill-count, and ng/ml for plasma varenicline; Catz et al., 2011).

Integrity of the Blind

Participants may be likely to notice a change in their physiological and/or psychological state that would be best noted following the two-week washout period (Week 14), and their perception may change after they experience the second potential washout period (Week 26). This follows the questions outlined by [name] et al. (2008).

Program Satisfaction

Given the negative perception that many individuals have of Chantix, understanding patient's satisfaction with the program, and how that might change between weeks 12 (standard duration) and 24 (extended duration), will provide a basis for clinical relevance. These questions were modeled after patient satisfaction questionnaires used for a variety of smoking cessation programs.

Outcomes Variables.

Abstinence (primary)

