Aim 1: The primary analysis is a comparison in Week 24 and Week 52 point prevalence quit rates between standard and extended therapy. For the week 24 comparison, we based our sample size on the expectation that the quit rate in the standard arm would be equal to the Week 24 quit rates reported in past clinical trials of varenicline for participants who received 12 weeks of treatment (i.e., 33%; Gonzales et al., 2006). We also expect to see at least the same effect on week 24 quit rates here as we saw in our past extended treatment trial (i.e., an OR of 1.81 or a difference of ~14%; [name] et al., 2010b). Thus, we have 80% power (alpha .05) with a sample of 374 if the difference between treatment arms in Week 24 quit rates is 14% (i.e., Week 24 quit rates for extended therapy is 47%). For the Week 52 comparison, we can expect a Week 52 quit rate for the extended arm of 56% (Tonstad et al., 2006), vs. 28% for standard treatment (Gonzales et al., 2006), for which we have 99% power (alpha = .05) with n = 374; we are powered to detect a difference at Week 52 of 14% if the present study yields a smaller effect than expected based on past studies.

Aim 2: The primary analysis is a comparison in Week 24 and Week 52 differences in QOL and severe side effects. For QOL, we have 80% power to detect a mean difference of 0.87 in physical QOL and a mean difference of 1.2 in mental QOL at any time-point, effects seen previously ([name] et al., 2010a). For side effects, the analyses will involve a test of non-inferiority since we cannot use standard statistical tests and conclude that a non-significant comparison means that the treatments are equal (i.e., “the absence of evidence is not evidence of absence”). In our past bupropion study ([name] et al., 2010a), 95% of placebo and 88% of bupropion participants reported no severe side effects. Assuming a similar difference, we have 90% power to detect equivalence with a floor of 80%, or an extended group that is 15% < the standard group.

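### The Aim 2 severe-side-effect comparison has no defined window and does not isolate Day 85 to Day 168, the only period in which the arms receive different drug

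*Combined protocol and SAP*

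**What the plan says.** The only text that attaches time-points to this comparison is Statistical Analysis, Power, Aim 2: "The primary analysis is a comparison in Week 24 and Week 52 differences in QOL and severe side effects". The same paragraph says "For side effects, the analyses will involve a test of non-inferiority". It takes its planning rates from an earlier bupropion trial ("95% of placebo and 88% of bupropion participants reported no severe side effects") and concludes "we have 90% power to detect equivalence with a floor of 80%, or an extended group that is 15% < the standard group".

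Data Analysis, Aim 2 words it differently: "We will compare treatment arms in terms of the frequency of severe side effects (individual and total"). It names no visit and no window. It then describes a logistic regression against a lower boundary on the percentage without severe effects, and a test of whether the odds ratio lies outside a prescribed range. No odds-ratio limit is given.

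On treatment, the dosing text gives both arms the same active drug through Day 84. The standard arm moves to placebo on Day 85, and "Participants will take this medication until Day 168". Under Treatment Measures, Side Effects, "dose reductions or suspension of medication may be indicated based on the side effect reporting". The Potential Study Risks section also allows dose reduction or discontinuation.

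Table 2 schedules the side-effect checklist at every visit from Pre-Quit to Week 52, including Weeks 14, 18, 24 and 26.

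**The concern.** Aim 2 is meant to show that 12 more weeks of varenicline add no material severe harm. Only events that can reflect those 12 weeks inform that question.

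A Week 24 snapshot may not see a severe effect reported at Week 14 or 18 if drug was then reduced or stopped and the effect resolved. Drug-caused events of this kind arise mainly in the extended arm, so the loss is mostly one-sided. At Week 52 both arms have long been off active drug. In a non-inferiority test, anything that pulls the arms together makes success easier.

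A whole-trial count has a different weakness, because it mixes in 84 days on which the arms received identical treatment. With the window left open, it could also be settled after the results are known.

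**Working it through.** **Inputs.** From the plan: 374 participants; 95% and 88% free of severe side effects; floor 80%, a 15-point margin. Assumed: 1:1 allocation (187 per arm) and one-sided alpha 0.025. The plan says "All comparisons are 2-sided" but gives no alpha for the non-inferiority test.

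**1. The plan's own 90% power.**
- Two-arm test: SE = √(0.95×0.05/187 + 0.88×0.12/187) = 0.0286, and (0.15 − 0.07)/0.0286 = 2.80. Power is Φ(2.80 − 1.96) = 79.8% at one-sided 0.025, and Φ(2.80 − 1.645) = 87.5% at one-sided 0.05.
- One-sample exact test of the extended arm against 80% at one-sided 0.05: it passes if at least 159 of 187 are free of severe effects. Power is 91.0%.

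Only the one-sample version comes close to 90%, so the plan leaves the test itself open as well as the window.

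**2. Timing.** Week 52 is Day 364. 364 − 168 = 196 days, or 28 weeks after the last scheduled dose. 364 − 84 = 280 days, or 40 weeks after the standard arm's last active dose.

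**3. Visit-status reading.** Set true harm over Day 85 to Day 168 at the plan's limit: 5% standard, 20% extended. If a fraction v of the excess is still visible at Week 24, the extended arm shows 5% + 15%×v. The chance that the Wald upper 97.5% bound on the risk difference falls below 15 points, by exact enumeration:

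| v | Extended arm at Week 24 | False non-inferiority |
|---|---|---|
| 100% | 20.0% | 2.9% |
| 90% | 18.5% | 7.5% |
| 70% | 15.5% | 32% |
| 50% | 12.5% | 73% |

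The normal approximation gives 2.5% at v = 100%, 6.7% at 90% and 74% at 50%. At Week 52, with no remaining difference (5% in each arm), the test passes more than 99.9% of the time.

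**4. Whole-trial reading.** Let c be the Day 1 to Day 84 risk, equal in both arms and independent of later events. Each arm's risk becomes 1 − (1 − c)(1 − p), with p = 5% or 20%. The odds-ratio limit implied by 20% against 5% is (0.20/0.80)/(0.05/0.95) = 4.75, which is an assumption.

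| c | Standard | Extended | Difference | Odds ratio | False pass, risk difference | False pass, odds ratio |
|---|---|---|---|---|---|---|
| 5% | 9.75% | 24.0% | 14.25 | 2.92 | about 4% | 37–39% |
| 10% | 14.5% | 28.0% | 13.5 | 2.29 | about 6% | 76–78% |
| 20% | 24.0% | 36.0% | 12.0 | 1.78 | about 9% | 98–99% |

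The ranges in the last column reflect two separate calculations. With Day 85 to Day 168 events only, the odds-ratio test passes falsely about 3% of the time.

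**5. Whole-trial reading against the fixed 80% floor.** With c = 5%, the extended arm is 0.95 × 0.80 = 76% event-free and passes 0.2% of the time, against 4.8% at 80%. At the planned 88%, it falls to 0.95 × 0.88 = 83.6% event-free, and the pass rate drops from 91% to 34%. Here the added events make success harder.

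**The case against.** A reader might infer that the plan commits to a snapshot and is therefore shown to be biased toward finding no extra harm. The documents do not support that.

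- **Cumulative counting is a fair reading.** Data Analysis, Aim 2 speaks of frequency. Treatment Measures says overall frequency is tracked, and the planning rates name no visit. The checklist's recall period is not stated, so even a Week 24 report need not describe that day alone.
- **Not every reading favours success.** Whole-trial counting dilutes the odds ratio strongly and the risk difference slightly, and makes a fixed 80% floor harder to meet.
- **The visible fraction is assumed.** The documents give no value for it. With little resolution, the inflation is modest.
- **Week 52 may do no damage.** It misleads only if it is pooled with Week 24 or can support the claim alone. If both visits must pass, it cannot raise false success. The plan does not say how they combine.
- **Events before Day 85 arise on identical drug.** Missing them does not bias the absolute difference between arms. The snapshot problem is confined to Weeks 12 to 24.

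All of this stands. It changes the finding from a proven bias to an undefined endpoint with some unsafe readings. It does not supply a window. The monitoring board's comparison of side-effect increases by arm protects participants during the trial but does not define this test.

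**Conclusion.** The point holds as an undefined endpoint. The power and analysis sections give different accounts of when severe side effects are counted, and neither isolates the period of differing treatment. On the visit-status reading, a between-arm test is pulled toward non-inferiority. On the whole-trial reading, the direction depends on whether the odds ratio, the risk difference or the fixed floor is tested.

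The size is not known. The rise from about 3% to 7.5%, 32% or 73% assumes 187 per arm, one-sided 0.025, a risk-difference test, true harm exactly at the 15-point limit, and 90%, 70% or 50% of the excess still visible. It is a sensitivity range and not an estimate. The Week 52 figure of more than 99.9% shows only that Week 52 carries almost no information on this question. Because Aim 2 is a stated safety aim and the necessary data are already scheduled, the window should be fixed before analysis.

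**What to change.** In both Aim 2 paragraphs (Power and Data Analysis), define the safety endpoint as at least one severe side effect reported at any assessment after Day 84 through Week 26, that is, Weeks 14, 18, 24 and 26. A Week 12 visit held after Day 84 contributes only events that occurred after Day 84. Count the event whether or not drug was later reduced or stopped. Include severe effects already present at Day 84 that persist, since persistence on continued drug is part of the harm in question. A version restricted to effects new or worsened since Day 84 would drop those and should be a sensitivity analysis only.

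Run the between-arm non-inferiority test on this endpoint. State its scale, its alpha and the handling of missing side-effect reports, because the plan's missing-data rule covers smoking status only. Report Day 1 to Day 84 (arms pooled) and Week 52 descriptively, with neither able to support the non-inferiority claim.

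The cost is wording; no new visits or data are needed. Non-inferiority becomes somewhat harder to show. At the planned 95% and 88%, the two-arm risk-difference test has 79.8% power at one-sided 0.025 or 87.5% at 0.05, and the plan should say so in place of 90%.
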